8.10.3 STUDY CLOSE-OUT REPORTS

Any Clinical Study Report (final study report), abstracts or literary articles that are a result of the study should be sent to Merck Pharmaceuticals for review.

9.0 PROCEDURES FOR REPORTING UNANTICIPATED PROBLEMS INVOLVING RISKS TO SUBJECTS OR OTHERS, INCLUDING ADVERSE EVENTS (UPIRSOS)

9.1 Expedited Reporting of UPISROs Occurring at Yale

AEs classified as "serious" and "unexpected" that are possibly, probably, or definitely attributed to drug administration, or SAEs whose frequency exceeds expectations, require expeditious handling and reporting.

Serious Adverse Event (SAE)

Any adverse event that results in any of the following outcomes:

- death,
- a life-threatening experience,
- inpatient hospitalization or prolongation of existing hospitalization,
- a persistent or significant disability/incapacity,
- a congenital anomaly/birth defect, or
- any other adverse event that, based upon appropriate medical judgment, may jeopardize the subject's health and may require medical or surgical intervention to prevent one of the other outcomes listed in this definition.

The PI will promptly investigate all safety information related to an adverse experience. If the results of the PI's investigation show an adverse drug experience not initially determined to be reportable (based on whether the event is serious, unexpected, and associated with drug administration) is so reportable, the PI will report

such experience. Follow-up information to a safety report shall be submitted as soon as the relevant information is available.

SAEs will be reported in accordance with all applicable institutional (HIC), Sponsor, and FDA requirements. The Multi-site PI (Sponsor) will adhere to 21CFR56.108.

Reporting to the Yale Human Investigation Committee

Timeframe for Reporting

- 1. Events that may require a temporary or permanent interruption of study activities by the Principal Investigator or sponsor to avoid potential harm to subjects should be reported to the IRB **immediately** (if possible), followed by a written report to the IRB using the UPIRSO Reporting Form (710 FR 4) **no more than 5 calendar days** after the Yale Principal Investigator becomes aware of the event.
- 2. Internal Events (defined above) should be reported to the IRB using the UPIRSO Reporting Form (710 FR 4) within 5 calendar days of the Principal Investigator becoming aware of the event.
- 3. External Events (defined above) should be reported to the IRB using the UPIRSO Reporting Form (710 FR 4) within 15 calendar days of the Yale University Principal Investigator (PI) becoming aware of the event ONLY IF either of the following are true:
 - (a) The Yale PI has concluded that an immediate change to the protocol is necessary to address the risks raised by the event, and BI agreed to the changes OR
 - (b) A monitoring entity (e.g., an external IRB at the site where the problem or event occurred, the sponsor, or the Data Safety Monitoring Board) has required modifications/amendments to the research protocol or consent documents as a result of the event.

For all reports of external events, the UPIRSO Reporting Form (710 FR 4) must include the following information:

- (a) a clear explanation of why the event or series of events has been determined to meet criteria for reporting;
- (b) a description of the proposed protocol changes and any corrective actions to be taken by the PI in response to the external event; and
- (c) any aggregated data and an analysis or summary from the sponsor or DSMB, when applicable and available, sufficient to explain the significance of the event or series of events in order to ensure the information is interpretable and relevant to the IRB's task of protecting the rights and welfare of human participants.

Reporting to Investigators at Collaborating Sites

The Yale PI will notify all participating investigators in a written safety report of any adverse experience **associated with the use of the drug** that is both **serious** and **unexpected** as soon as possible and in no event later than 15 calendar days after the sponsor's (PI's) initial receipt of the information. [21CFR312.32(c)]

9.2 SUB SITE INVESTIGATOR SAE REPORTING REQUIREMENTS

The collaborating investigator (Sub Site PI) in a multi-center trial will report **serious**, **unexpected** adverse events occurring at their site to the Yale Principal Investigator **regardless of attribution** immediately (if possible) of knowledge of the event. Full written reports should be submitted to the Yale PI within 5 calendar

days of initial knowledge of the report. This information will also need to be recorded in Oncore Clinical Trials Management System in the SAE section.

Send SAEs to the Yale Principal Investigator:

Name: [name] [contact] Email: [contact] [contact]

9.3 SAE reporting to Merck

SAE reports and any other relevant safety information are to be forwarded to the Merck Global Safety [contact]:

• within two (2) calendar days upon receipt of initial and follow-up SAEs containing at least one fatal or immediately life-threatening event;

• within ten (10) calendar days upon receipt of any other initial and follow-up SAEs.

At all times, the Remote Monitoring Coordinator is available to facilitate submissions and answer any questions regarding the process for all sub site staff.

10.0 MULTI-SITE MANAGEMENT AND COORDINATION

10.1 Overview

This is a multi-site trial where **[name]** is the lead Principal Investigator for Yale University and for all non-Yale sites. The Gynecological Oncology research team at Yale University consisting of a Multisite Research Coordinator, Remote Monitoring Coordinator, Multi-site Data Manager, Clinical Research Nursing Coordinator, Specimen Procurement Coordinator and a Multi-site Administrative Assistant will provide multicenter research support for all sites involved in this project. The YCCI clinical trials management support staff will provide clinical database systems support and training through the use of Oncore Clinical Trials Management System.

10.2 Initiation of Study

Once sub-site IRB approval has been obtained and all required start up documents have been submitted, [name] will perform a Site Initiation Visit (SIV) prior to enrollment of study subjects. This will be either on-site or via teleconference with each participating site PI and staff available. Members of the Gynecologic Oncology research team will be available to answer all protocol questions. Once this has taken place with the participating site they may enroll subjects into the protocol. All pre and post SIV documents will be collected and stored in accordance with the Gynecologic Oncology Research SOP for collection of regulatory documents.

10.2.1 Investigational Site Training

[name] or an appointed designee will provide investigational staff training prior to study initiation. Training topics will include but are not limited to: Good Clinical Practice (GCP), AE reporting, study details and procedure, study documentation, specimen procurement and shipping, informed consent, and

enrollment. Sub sites are supplied with telephone and e-mail contact for all personnel and encouraged to contact with any questions regarding the conduct of the protocol.

10.2.2 Data Collection

Sites will use Oncore Clinical Trials Management System for all data associated with the protocol. Data managers at participating centers will receive Oncore access once they are designated by the site PI, complete an Oncore access request and submit HIPAA training certification. Individuals will receive Oncore training by a member of the YCCI clinical trials management support staff. Subjects entered into the system will be identified by a subject number assigned after randomization. The confidentiality of records that could identify subjects will be protected, respecting the privacy and confidentiality rules in accordance with the applicable regulatory requirement(s). The database will be monitored by the Multi-site Data manager and the Remote-site Monitoring Coordinator to ensure that data is entered in a timely manner.

10.3 Monitoring

[name] or an appointed designee must be allowed to visit all study site locations periodically to assess the data quality and study integrity. On-site they will review study records and directly compare them with source documents, discuss the conduct of the study with the investigator, and verify that the facilities remain compliant.

In addition, remote monitoring of data may be performed periodically requiring the site to submit de-identified patient data for comparison to the Remote-site Monitoring Coordinator. The study may be audited by the Yale University DSMB internal auditors. Yale University DSMB audit reports will be kept confidential.

10.4 Study Enrollment Procedures

Any modification of the original consent document provided to participating sites by the Coordinating Center must be approved in advance by the Coordinating Center. Rationale will be provided with any request for a change. A copy of each site's IRB and Coordinating Center approved informed consent document must be on file at the Gynecological Oncology Regulatory office before subjects may be enrolled.

To register eligible patients on this study, each site will contact the Multi-site Coordinator; [name] [contact]) or [name] [contact]) and provide the signed and dated eligibility checklist, completed signature page of the consent form and additional source documents if requested by the Principal Investigator or Multi-site Coordinator. Once the Principal Investigator or Multi-site Coordinator verifies eligibility, a unique subject study number will be issued. The subject will not be identified by name.

10.5 Responsibilities of the Lead Investigator [name]:

The lead investigator is responsible for the overall conduct of the study at all participating sites and for monitoring the safety and quality of the data as well as compliance to the protocol and with applicable federal regulations and Good Clinical Practice (GCP).

The lead investigator will monitor accrual rates at all sites for adequate progress.

The Lead Investigator will ensure appropriate coordination, submission and approval of the protocol as well as the consent documents and any subsequent amendments at all sites. There will be only one version of these documents that will be used by all participating institutions and the lead investigator is responsible for assuring that the correct versions are used by all participating institutions.

No additional sites will be added to the study without a proposed amendment and review and approval by the Yale IRB (HIC).

The lead investigator has the authority to suspend accrual at any site not complying with this protocol, including not submitting data in a timely manner. Any suspension of accrual will be reported to the Yale University Data Safety Monitoring Committee (DSMC) as well as to the Yale University HHRP. Site principal investigators must report the suspension to their IRB.

10.6 Responsibilities of the Coordinating Center

The coordinating center, under the direction of the lead investigator [name], MD, is responsible to ensure that each participating site has the appropriate assurance on file with the Office for Human Research Protection (OHRP) or their local/central Institutional Review Board (IRB). The coordinating center is responsible for obtaining copies of OHRP/IRB assurance for each site prior to enrollment of subjects at the site.

10.7 IRB Approvals

The Coordinating Center is responsible to ensure that no patients are entered on study without full IRB approval and that IRB re-approval is appropriately maintained. A copy of the IRB approval document from each participating institution will be obtained by the Coordinating Center prior to activation of the study at any site. Documentation of reapproval must be provided to the Coordinating Center in a timely manner or registration will be halted at any site in which a current continuing approval is not on file at the Coordinating Center.

10.8 Amendments and Consents

The Coordinating Center will maintain a copy of all amendments, consent forms, and approvals from each site. Consent forms will be reviewed and approved by the Coordinating Center to ensure consistency with the Yale IRB approved consent. Should changes to the protocol or consent become necessary, protocol amendments will be issued by the Coordinating Center to all sites for local site approval prior to implementation, unless there is an apparent immediate hazard to a subject or the subject's best interest is endangered. Any such deviation from the approved protocol will be promptly reported to the lead investigator.

10.9 Responsibilities of Participating Sites:

The principal investigator at each site is responsible for the overall conduct of the study at their site and for monitoring the safety and quality of the data as well as compliance to the protocol and with applicable federal regulations and (GCP).

The principal investigator at each site is responsible for assuring that all the required data is collected and entered onto the e-CRFs using Oncore Clinical Trials Management Systems in accordance with study-specific requirements and that the data submission and reporting timelines are met. The coordinating center will perform onsite monitoring periodically to ensure adherence to the protocol as well as regulatory compliance.

11 STATISTICAL ANALYSIS PLAN

a. Statistical Analysis Plan

This is a single-arm, open-label phase II study using the optimal flexible two-stage design of Chen *et al.* (24) to evaluate the efficacy of the study regimen through objective tumor response. There are no treatment comparisons involved and no known historical controls available.

The targeted accrual for the first stage of the study will be 12 eligible and evaluable patients but permitted to range from 8 to 15 for administrative reasons. The cumulative targeted accrual for the second stage will be 22 eligible and evaluable patients but permitted to range from 18 to 25 for administrative reasons.

If the true probability of tumor response is 5%, then the study has a 65% average probability of early termination and an expected probability of 10% of incorrectly declaring the study regimen interesting. If the true probability of tumor response is 25%, then the study has an expected 90% chance of correctly classifying the study regimen as being interesting.

11.0 Justification of Design:

This study will employ the optimal flexible two-stage design since it not only minimizes the average expected number of patient exposure to inactive regimen, but also allows the actual study accrual to slightly deviate from the targeted study accrual in a multi-center trial while maintaining the levels of the average type I and II errors.

Study Endpoints

11.1Primary Endpoints

1) Frequency of objective tumor response as assessed by RECIST. Subjects who continue treatment beyond initial investigator-assessed, RECIST 1.1-defined progression will be considered to have investigator-assessed progressive disease at the time of the initial progression event but may be designated as delayed responses for purposes of determining proportion of objective response and counted as responses for two stage designs.

2) Frequency and severity of adverse events as assessed by CTCAE v4.

Secondary Endpoints

1) Duration of progression-free survival (PFS) and overall survival (OS).

Translational Science Objectives

- 1) To prospectively evaluate and compare the sensitivity/specificity of NGS and comprehensive genomic profiling (CGP) to assess MMR gene deficiency/microsatellite instability (MSI) to standard PCR-based DNA microsatellite instability (MSI) and immunohistochemistry (IHC) testing for the identification of patients responsive to pembrolizumab. B) To evaluate the tumor mutation burden (TBN) and individual characteristics of somatic mutations identified using whole exome sequencing (WES) in ultra and hypermutated patients and their correlations to OR, PFS and OS in pembrolizumab-treated patients.
- 2) To explore the composition of immune infiltrates in POLE/POLD1 and MMR defective tumor specimens/biopsies from primary and/or metastatic/recurrent sites with selected markers including (but not limited to) CD4+,CD8+, FoxP3, CD25, LAG-3, TIM-3, and ICOS and their correlations to OR, PFS and OS in pembrolizumab -treated patients.

- 3) To systematically evaluate PD-1 and B7-H1 (i.e., PD-1 Ligand) expression in tumor infiltrating lymphocytes (TILs) and tumor cancer cells, and explore their correlations with OR, PFS, and OS in pembrolizumab -treated patients with PD-1 and B7-H1 scoring results.
- 4) To explore the association with treatment and subject response in peripheral blood populations in ultramutated and hypermutated patients before and during pembrolizumab treatment, including absolute lymphocyte counts, number of T cells, T-cell subsets, NK cells, and B cells as well as their cellular phenotypes by flow cytometry.

Primary Objectives Study Design

Primary Hypothesis and Endpoints

Primary Hypothesis:

The intent of this study is to evaluate the efficacy of the study regimen measured by objective tumor response. Tumor response is dichotomized as response (i.e., complete or partial response) vs. non-response (i.e., stable disease, progressive disease, or indeterminate disease) and is assumed to have a Bernoulli distribution with a probability equal to π . Given a sample size, the number of tumor responses is binomially distributed with a given sample size and probability equal to π . Statistically, the evaluation of the study regimen efficacy measured by tumor response will be formulated through hypothesis testing via tumor response.

We will target an accrual of 12 eligible and evaluable patients in the first stage of the study, but permit the accrual to range from 8 to 15 for administration reasons. If there are more than 0 out of 8-13 or 1 out of 14-15 patients responding (complete or partial response) and medical judgment indicates, accrual to the second stage of the trial will be initiated. Otherwise, the study will be stopped and the treatment will be classified as clinically uninteresting. If the study advances to the second stage, then a cumulative accrual of 22 eligible and evaluable patients will be targeted, but permitted to range from 18 to 25 for administration reasons. If more than 1 out 18, or 2 out 19-25 patients respond and medical judgment indicates, then the study regimen will be considered worthy for further investigation.

Under the assumed accrual ranges of 8 to 15 (stage 1) and 18 to 25 (cumulatively after stage 2), and under the rejection rules associated with these accrual ranges, if the true probability of tumor response is 5%, then the study has a 65% average probability of early termination and an average 10% probability of incorrectly declaring the study regimen interesting; if the true probability of tumor response is 25%, then the study has a 90% average chance of correctly classifying the study regimen as being interesting.

Table 8: Accrual Ranges and Associated Rejection Rules.					
Stage of Accrual	Targeted Cumulative Accrual	Limits of Actual Accrual	Max Number of Responses to Reject Study Regimen		
1	12	8-15	0/(8-13), 1/14-15		
2	22	18-25	1/(18), 2/(19-25)		

The following table (Table 8) summarizes the accrual ranges and associated rejection rules.

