APPENDIX C- Specimen Shipping Instructions

1.0 OBJECTIVES

Primary Objectives & Hypothesis

Hypothesis: Because POLE/POLD1-ultramutated and/or hypermutated/MMR-defective endometrial tumors harbor a large number of novel mutations and are heavily infiltrated with TIL, anti-PD1 therapy with Pembrolizumab may represent an ideal treatment option for these patients to re-invigorate pre-existing immune responses and eliminate residual/recurrent chemotherapy and radiation resistant disease.

1.1 Primary Objectives:

- **1.1.1** To assess the antitumor activity (proportion of objective response by RECIST 1.1 criteria) of pembrolizumab with objective tumor response in patients with persistent, recurrent or metastatic endometrial cancer harboring an ultra-mutated or hyper-mutated (MMR gene-defective) phenotype identified by next generation sequencing (NGS) and comprehensive genomic profiling (CGP).
- **1.1.2** To determine the nature and degree of toxicity of pembrolizumab as assessed by CTCAE in patients with persistent, recurrent or metastatic endometrial carcinoma

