7.0 EVALUATION CRITERIA

7.1 Objective Response

The major parameters of response to be assessed include complete and partial responses, Progression-Free Survival, Overall Survival, documentation of Sites of Recurrence, and Treatment Related Toxicity. Treatment response will be based on RECIST v1.1 Guidelines for Measurable Lesions.

Measurable Lesions- Only recurrent patients with measurable lesions will be enrolled in the study. All target lesions must be assessed using the same technique as baseline. Included in the evaluations are the following standard response criteria for target lesions:

- Complete Response (CR): Disappearance of all target lesions. No new lesions. Lymph nodes must be <10mm short axis.
- Partial Response (PR): At least a 30% decrease in the sum of the longest diameter of target lesions, taking as reference the baseline sum of the longest diameters. No new lesions.
- Progressive Disease (PD): The appearance of a new lesion, or at least a 20% increase in the sum of the longest diameters of the target lesions, taking as the reference the smallest sum of the longest diameters recorded since treatment started, and at least 5mm increase.
- Stable Disease (SD): Target lesions do not qualify for CR, PR, or progression. No new lesions.

All non-target lesions must be assessed using the same technique as baseline. Included in the evaluations are the following standard response criteria for non-target lesions:

- Complete Response: The disappearance of all non-target lesions.
- Incomplete Response/Stable Disease: The persistence of one or more non-target lesion(s).
- Progression Disease: The appearance of one or more new lesions and/or unequivocal progression of existing non-target lesions.

Objective Response (OR) will be defined as Complete or Partial Response using CR or PR as described by the above RECIST v1.1 Response Criteria.

Progression-Free Survival (PFS) will be defined as date from entry to a particular protocol to date of reappearance or increasing parameters of disease on imaging (CT scan or MRI) or by clinical exam or death from any cause, or is censored at date of last disease assessment.

Overall Survival (OS) will be defined as observed length of life from entry to a particular protocol to death or, for living patients, date of last contact.

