11.2 Definitions of Primary Endpoints and How These Will Be Analyzed

- 1) Proportion of objective tumor response as assessed by RECIST.
- 2) Frequency and severity of adverse events as assessed by CTCAE v4 and corresponding frequency table will be provided as descriptive statistics.

All patients who receive any therapy will be evaluated for both treatment efficacy and toxicity. Only those patients who are deemed "ineligible" or who receive no therapy will be eliminated from the analysis. While on occasion, circumstances may prevent the determination of treatment efficacy, such patients will be included in the analysis and labeled as "indeterminate." This category will be listed and be reflected in the calculation of the proportion responding.

11.3 Sample Size and Power Calculations:

The sample size and power calculations will be based on the optimal flexible two-stage method (24). This method assumes that the number of patients responding to the study regimen has binomial distribution and the accrual combination for stage 1 and 2 is uniformly distributed.

The minimum and maximum accruals for this study are 8 and 25 eligible and evaluable patients, respectively.

Under the assumed accrual ranges of 8 to 15 (stage 1) and 18 to 25 (cumulatively after stage 2), and under the rejection rules shown in **Table 8** for these accruals, the study has an average power of 90.0% at a target alpha=10% significance level to detect the 20% increase in the rate of tumor response from the null-hypothesis rate of 5% to a clinically interesting rate of 25% under the alternative hypothesis. The study's true alpha has an average of 9.5% with a 64.9% average probability of early termination and average expected sample size of 15.14 subjects under the null hypothesis.

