11.4 Study Monitoring of Primary Objectives

There will be one formal futility interim analysis for treatment efficacy in the study.

If the study has an accrual of 12 eligible and evaluable patients in the first stage since the study is activated, which is permitted to range from 8 to 15, the accrual of the study will be temporarily suspended until the data of primary endpoint is matured to make a decision on whether to go forward to second stage accrual according to the guidelines. That is, if there are 0 out of 8-13 or at most 1 out of 14-15 patients responding (complete or partial response) and medical judgment indicates, the study will be stopped and the treatment will be classified as clinically uninteresting. Otherwise, accrual to the second stage of the trial will be initiated. As this is a two-stage multi-institutional phase II protocol, the initial overall review of toxicity is usually performed after completion of the first stage of accrual, at which point accrual is generally suspended pending formal analysis of response.

Accrual Goal

The projected minimum and maximum accruals for the study are 8 and 25 eligible and evaluable patients, respectively. The targeted accrual is 12 eligible and evaluable patients in the first stage of the study, and cumulatively 22 eligible and evaluable patients will be targeted in the second stage if the study advances.

Study Duration

1) Patients will receive therapy until disease progression or intolerable toxicity intervenes.

The patient can refuse the study treatment at any time.

2) All patients will be treated (with completion of all required case report forms) until disease progression, initiation of a subsequent cancer treatment or study withdrawal.

Patients will then be followed every three months for the first two years and then every six months for the next three years.

3) A patient is considered off study therapy when the patient has progressed or died, a nonprotocol drug or therapy (directed at the disease) is initiated, or all study therapy is discontinued. Report all treatment received on Cycle Drug Information Forms and adverse events on Adverse Events Forms until the patient qualifies as being off study therapy.

Estimated Duration for Completion of Primary Endpoint: provision of timeframe, e.g. 24 months from activation

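### Section 11.1 lets patients with RECIST 1.1 progression be counted as delayed responders at discretion and without criteria, so the same data can give two Table 8 decisions

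*Combined protocol and SAP*

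**What the plan says.** The documents describe the primary response endpoint in several places.

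- Objective 1.1.1 refers to the "proportion of objective response by RECIST 1.1 criteria".
- Section 7.1: "Objective Response (OR) will be defined as Complete or Partial Response using CR or PR as described by the above RECIST v1.1 Response Criteria". Its partial-response entry requires a 30% decrease, "taking as reference the baseline sum of the longest diameters. No new lesions".
- Primary hypothesis, section 11: "Tumor response is dichotomized as response (i.e., complete or partial response) vs. non-response (i.e., stable disease, progressive disease, or indeterminate disease".
- The decision rules after the primary hypothesis and in 11.4 count complete or partial responses. The final rule reads "If more than 1 out 18, or 2 out 19-25 patients respond and medical judgment indicates", in which case the regimen goes forward. Section 11.2 repeats that response is assessed by RECIST. None of these mentions delayed responses.
- Section 11.1 is the exception. Patients who continue past first RECIST 1.1 progression are progressive disease at that event, but "may be designated as delayed responses for purposes of determining proportion of objective response and counted as responses for two stage designs".

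On timing, 11.4 says that after stage 1 "the accrual of the study will be temporarily suspended until the data of primary endpoint is matured to make a decision". On follow-up, 6.1.1.11 continues imaging until RECIST 1.1 progression, and the follow-up text in 6.1 moves patients to survival contact after progression. The trial summary and 11.4 describe treatment until progression, while 4.8 requires discontinuation at confirmed radiographic progression.

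**The concern.** A patient who progresses and later shrinks can be a non-responder under 7.1 and the primary hypothesis, and a responder under 11.1. Section 11.1 makes the choice optional and does not say who makes it or by what measurement. Section 7.1 fills the gap only in part. If first progression was growth of target lesions, a later 30% decrease from baseline could meet the PR wording, although nothing says that wording applies after progression. If first progression was a new lesion, the PR wording cannot be met.

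The trial is open-label, progression is investigator-assessed, and scheduled imaging stops at progression. The data behind a designation would therefore be collected unsystematically, by people who know the running count. Table 8 works with limits of 0, 1 or 2 responses, so a single call can decide both the stage 1 decision and the final verdict. It also changes the reported response proportion, whatever the true rate.

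**Working it through.** **Inputs.** Null and alternative rates 5% and 25%; accrual 8-15 (stage 1) and 18-25 (cumulative); all accrual combinations equally likely (11.3). Maximum responses to reject: r1 = 0 for n1 = 8-13 and 1 for n1 = 14-15; r2 = 1 for n = 18 and 2 for n = 19-25 (Table 8). The delayed-response rate d is not in the documents and is assumed below.

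**Formulas.** With b(x; m, p) the binomial probability:

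- Early termination = sum over x = 0..r1 of b(x; n1, p).
- P(declared interesting) = sum over x > r1 of b(x; n1, p) × P[Bin(n − n1, p) ≥ r2 + 1 − x].
- Average both over the 8 × 8 = 64 accrual pairs.

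**Step 1: reproduce the plan.** Section 11.3 states that the "true alpha has an average of 9.5% with a 64.9% average probability of early termination", with power 90.0% and expected sample size 15.14. Enumeration gives average alpha 9.45%, early termination 64.9%, power 90.05% and expected size 15.13. The design arithmetic is sound for one fixed endpoint.

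At the target 12/22 with p = 0.05, P(0/12) = 0.95^12 = 0.5404, and

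alpha = 0.3413 × 0.0861 + 0.0988 × 0.4013 + 0.0196 × 1 = 0.0294 + 0.0396 + 0.0196 = 0.0886.

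**Step 2: one data set, two decisions.**

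| Data | CR/PR only | With delayed response |
|---|---|---|
| Stage 1, n1 = 12: 0 CR/PR + 1 delayed | 0/12, stop | 1/12, continue |
| Stage 1, n1 = 14: 1 CR/PR + 1 delayed | 1/14, stop | 2/14, continue |
| Final, n = 22: 2 CR/PR + 1 delayed | 2/22, reject | 3/22, worth further study |

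**Step 3: illustrative size.** Suppose the 5% null means CR/PR without delayed responses. The counted rate is then 0.05 + d. The inclusive count can only add responses, so a trial that succeeds on CR/PR alone also succeeds on the inclusive count. The probability that the two counts give different final verdicts is therefore the difference between the two success probabilities. This takes stage 1 delayed responses as known at the stage 1 review.

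| Assumed d (points) | Average alpha | Alpha at 12/22 | Verdicts differ at 12/22 |
|---|---|---|---|
| 0 | 9.45% | 8.86% | 0 |
| 0.25 | 10.48% | 9.91% | 9.91 − 8.86 = 1.05% |
| 0.5 | 11.55% | 11.01% | 11.01 − 8.86 = 2.15% |
| 1 | 13.81% | 13.35% | 13.35 − 8.86 = 4.49% |
| 2 | 18.71% | 18.49% | 18.49 − 8.86 = 9.63% |

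At d = 0.25 the 12/22 alpha is still below the 10% target. With a CR/PR rate of 25% and d = 2 points, the final verdicts differ in 2.3% of trials at 12/22.

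These figures are for the numeric rule alone; the plan also requires medical judgment at each decision.

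**The case against.** The best defence is that 11.1 is an express, specific clause written in advance, and that it governs the general wording elsewhere. Much of this stands. Objective 1.1.1 names neither CR nor PR, and the decision rules speak of complete or partial response without excluding one seen after progression. A reader might infer that every other section counts only RECIST CR/PR before progression, but the documents do not go that far. The direct conflict is with 7.1 and with the listing of progressive disease as non-response. The defence does not supply a rule: an exception that may or may not be applied, with no criteria, does not fix an endpoint.

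A second objection is that delayed responses may be rare, because treatment and imaging largely end at progression. That is fair, and it is why no rate is asserted here. But 4.8 speaks of confirmed progression and 6.1 allows scans as medically indicated, so the opportunity exists.

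Third, maturity of the stage 1 data is undefined for ordinary responses too. That is correct. The clause adds to this problem because it sets no window for delayed responses.

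A reader might also measure the problem by how often trials finish exactly on a limit, such as the 54.0% of null trials at 0/12. That describes the cut-offs, not the clause. Nothing changes unless a delayed responder exists, and a trial rescued at 0/12 only continues: it then needs at least 2 responses in 10 more patients, with probability 8.6% at a 5% rate.

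**Conclusion.** The point holds as a definitional defect in the primary endpoint, not as an error in the sample size. As written, a discretionary call can reverse a Table 8 decision, and no section says which definition governs.

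A reader might infer that the trial's alpha is inflated. The documents do not support that as a fact: they give no delayed-response rate and do not say whether 5% and 25% include such responses. If 5% includes them, the stated 9.5% stands for the inclusive count. If it does not, assumed additions of 0.25, 0.5, 1 or 2 points move average alpha to 10.5%, 11.5%, 13.8% or 18.7%. The gap should be corrected; its numerical effect is illustrative.

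**What to change.** Replace the optional clause in 11.1 with one objective response definition for the primary proportion and Table 8. Use it in 7.1, 11.1, 11.2, 11.4 and the primary hypothesis, and state in 11.3 that 5% and 25% refer to it. Either option is workable:

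- **(a)** Count CR or PR by section 7.1 recorded before first RECIST 1.1 progression, and report later responses in a separate descriptive proportion.
- **(b)** Keep delayed responses under a rule fixed in advance: threshold against baseline, handling of new lesions, time window and assessor. Section 11.4 should then state when stage 1 data are mature.

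Under both, report the count with and without delayed responses. The document is Version 9.0 of April 2023, after the estimated trial end of June 2020, and accrual status is not stated. If response data have been reviewed, the change should be recorded as made after that point.

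The cost is text only; Table 8 and accrual stay as they are. Under (a) the reported proportion may be slightly lower. If 25% was meant to include delayed responses, average power under (a) falls from 90.05% to 88.4% at a 24% rate, or 86.6% at 23%.

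Separately, the trial summary and sections 4.8, 6.1, 6.1.1.11, 11.1 and 11.4 must be reconciled on treatment and imaging after progression. This point takes no position on which treatment rule is right.
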